8.13 Efficacy Analysis

When possible and according to age, the actual Faces scores and the change from baseline in Faces score for muscle stiffness, pain weakness and fatigue will be summarised over time.

Change from baseline in time (in seconds) to relaxation of hand muscles and reduction in relaxation time from the first to the third/fifth contraction and time (in seconds) for Timed-up and go (TUG) test will be summarised over time from screening to week 104.

Quality of life data will be presented descriptively by visit along with the change from baseline.

The observed values of Clinical Global Impression Scores and the change from baseline in Clinical Global Impression Score from baseline to Week 104 will be summarised.

The observed values of Myotonia Behaviour Scale Scores and the change from baseline in Myotonia Behaviour Scale Score from baseline to Week 104 will be summarised.

When performed, changes in clinical laboratory values from Screening to Week 104 will be summarised.

A separate Statistical Analysis Plan will be prepared.

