The number of patients in this study is not hypothesis driven; rather as agreed with PDCO, in that at least 10 evaluable subjects will be sufficient to assess efficacy and safety of mexiletine in this ultra-rare paediatric subpopulation for the age group of 0- 6 years old.

Statistical Analysis:

Summary descriptive statistics will be provided for all collected parameters. The categorical variables will be presented with frequency and percentages.

The analysis will be performed for all patients as well as by age cohort.

Overall data collected will be analysed to assess the safety and acceptability/palatability of different modes of mexiletine administration (i.e., capsule, sprinkled on food and/or gastric (enteral) tube where such formulations are used), and the factors that govern the route of administrations in paediatric patients.

If performed and available -as per the normal disease management of each participating site, and age-appropriate- the following will be analysed and presented:

- Change from baseline in time (in seconds) to relaxation of hand muscles and reduction in relaxation time from the first to the third/fifth contraction and time (in seconds) for Timed-up and go (TUG) test will be summarized.
- The actual Faces scores and the change from baseline in Faces score for muscle stiffness, pain, weakness and fatigue will be summarized.
- Quality of life data will be presented descriptively along with the change from baseline.
- The observed values of Clinical Global Impression (CGI) Scores and the change from baseline in CGI Scores assessed by the caregivers and investigators.
- The observed values of Myotonia Behaviour Scale (MBS) Scores and the change from baseline in MBS from baseline will be summarized.

The detailed statistical treatment of the data and any analysis methods will be specified in a

Statistical Analysis Plan (SAP)

TABLE OF CONTENTS

OR SIG	NATUR	E PAGE	2
SYNO	PSIS		
OF CO	NTENTS	S	
F TABL	.ES		
F FIGU	RES		
INTRO	DUCTIC)N	
1.1	Backgro	bund to myotonic disorders	
	1.1.1	Myotonic dystrophies type 1 and 2 (DM1 and DM2)	17
	1.1.2	Non-dystrophic myotonic disorders (NDM)	
	-		
2.1	Study O		
	2.1.1	The Primary objectives	25
	2.1.2	Secondary objectives	25
STUDY	DESIG	N	
3.1	Overall	Study Design	
3.2	Discussi	ion of Study Design	
	3.2.1	Appropriateness of Measurements	27
	3.2.2	Control Group	
	3.2.3	Duration of Study	
3.3	Selectio	n of Study Population	
	3.3.1	Inclusion Criteria	
	3.3.2	Exclusion Criteria	

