3.2 Discussion of Study Design

Study inclusion screening time will be approximately 2 weeks.

Patients who meet the eligibility criteria will be enrolled in two cohorts by age groups although cohorts are not planned to necessarily enrol sequentially (cohort definition is to assure minimum requirements for meeting PIP agreements).

- Cohort 1 Infants and children aged between 6 months to less than 6 years.
- Cohort 2 Neonates and infants from birth to less than 6 months.

The overall treatment duration follow-up for each cohort will be at least 2 years.

Dosing and treatment administration in this registry study should be done as per the treating physician clinical practice.

Visits to the clinic are to occur according to routine site's clinical practice, or when applicable according to the treating practice physician.

An initial visit (i.e., screening equivalent that will also serve as baseline) will take place to ensure the patient currently complies with all participation. This visit will serve for the patient to enter the study.

The end of treatment (EOT) visit will be the first routine clinical practice visit after at least 2 years have been completed since the patient entered the study (baseline visit) or 2 weeks after the last mexiletine intake after 2 years of treatment (whichever occurs first).

After 24 months, no study specific visits and data collection are required and patients will be treated and followed up as per the investigator's site protocol.

The following data elements will be collected during this registry, as permitted by the clinical site normal clinical practice for patients with myotonic disorders and according to the patient's age, using as the example other myotonia registries (Lagrue *et al.*, 2019).

- Demographics
- Genetics: DM1, DM2 or NDM corresponding clinical forms
- Musculoskeletal manifestations (myotonia, facial hypotonia)
- Orthopaedic deformities (spine, feet or hands, orthoses, back brace, specialized followup, surgery)
- Cardiorespiratory signs (non-invasive ventilation, sleep disorders, ECG / left ventricular ejection fraction (LVEF), pacemaker/defibrillator)
- Ophthalmic and endocrinologic manifestations (cataract, diabetes, thyroid disorders)
- Psychomotor development disabilities
- Gastrointestinal (GI) disorders
- Patterns of mexiletine use including dose/ frequency.

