6 ENDPOINTS AND VARIABLES

6.1 **Primary Variables**

The endpoints to assess efficacy (exploratory) will be adapted to the patient's age and the corresponding tests they are able to perform. When feasible the following will apply in accordance with standard clinical practice:

- Muscle strength measured using the modified Medical Research Council (MRC) scale to evaluate neck flexors, shoulder abductors, elbow flexors and extensors, wrist extensors, finger flexors, hip flexors, knee flexors and extensors, posterior foot flexors and plantar flexors.
- Clinical Global Impression (CGI) Scores given to caregivers and assessed by the investigators
- Number and frequency of adverse events (AEs), serious adverse events (SAEs) and AE leading to treatment discontinuation, throughout the study while on treatment with mexiletine
- Incidence of adverse events of special interest (AESI)
- Description over time of efficacy outcomes obtained from clinically indicated tests as per the treating physician typical clinical practice and according to patient's age and cohort.
- Any changes in frequency, treatment interruptions of mexiletine.

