The modified Medical Research Council (MRC) scale can be used to evaluate neck flexors, shoulder abductors, elbow flexors and extensors, wrist extensors, finger flexors, hip flexors, knee flexors and extensors, posterior foot flexors and plantar flexors (MRC, 1975; Verreydt *et al.*, 2022). The MRC scale of muscle strength uses a score of 0 to 5 to grade the power of a particular muscle group in relation to the movement of a single joint (score 0 corresponds to no contraction, 3 active movement against gravity and 5 equates to normal power).

VI. Paediatric Quality of Life Questionnaire (PedsQL)

Changes in health-related quality-of-life as measured by the PedsQLTM Quality of Life (version 4.0) and Neuromuscular modules (version 3.0). These multidimensional scales assess the frequency of health problems using generic and disease-specific approaches, respectively. Subjects and/or parent or proxies report a score of 0 to 4 (never to almost always) and questionnaires are tailored to age groups. The Quality of Life module consists of 23 questions that are further divided into physical, emotional, social and school functioning subsets. The 25-question PedsQLTM Neuromuscular module was created as a more specific tool to measure health-related quality of life for musculoskeletal diseases such as Duchenne's muscular dystrophy and Spinal Muscular Atrophy (Iannaccone *et al.*, 2009; Davis *et al.*, 2010). It is subdivided into symptom/function, communication and family resource dimensions. Greater scores indicate morbidity and illness burden compared to healthy controls, the latter scoring no less than 80 in all scales (Varni *et al.*, 2002).

VII. Clinical Global Impression (CGI) scores

This will be evaluated by a caregiver and by the investigator. Efficacy will be evaluated on a 4-point scale as very efficient, good, fair or poor.

VIII Acceptability of mexiletine administration

Acceptability of different modes of mexiletine administration (i.e., capsule, sprinkled on food and/or gastric (enteral) tube where such formulations are used), and the factors that govern the route of administrations in paediatric patients will be assessed by reviewing the patient records, interviewing patients and their caregivers. Any difficulty in swallowing or compliance will be noted and if capsules were opened and content was taken, details should be recorded accordingly.

IX Palatability

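### The CGI as defined rates how well treatment works, so its planned change from baseline does not exist for children starting mexiletine and does not measure benefit for those already on it

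*Protocol*

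**What the plan says.** Section 6.1 (Primary Variables) names two efficacy scales: the modified MRC muscle strength scale and "Clinical Global Impression (CGI) Scores given to caregivers and assessed by the investigators". The section labels efficacy as exploratory.

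Item VII of Assessment of Efficacy contains the whole definition of the CGI. On the raters it says "This will be evaluated by a caregiver and by the investigator", and on the scale "Efficacy will be evaluated on a 4-point scale as very efficient, good, fair or poor". The protocol describes no severity version and no separate version for use at entry.

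Section 8.13 plans two CGI summaries in one sentence: the observed values, and then "the change from baseline in Clinical Global Impression Score from baseline to Week 104 will be summarised". The synopsis makes the same pairing, with "The observed values of Clinical Global Impression (CGI) Scores and the change from baseline in CGI Scores", for both raters.

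Section 3.2 fixes the reference point: "An initial visit (i.e., screening equivalent that will also serve as baseline) will take place". Baseline is therefore entry to the registry, not the start of treatment. Inclusion criterion 4 (section 3.3.1) admits children already on mexiletine and children for whom the physician is only considering it.

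**The concern.** A change from baseline needs the same quantity to be measurable at both times. A scale that grades how well a drug works has no value before the drug is taken. The planned change therefore cannot be formed for children who start at or after enrolment. For the others it answers a different question from the one a reader would assume.

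What is at stake is the interpretation of a listed primary variable in a registry with a minimum of 10 evaluable patients. A reader of the final table would naturally take a CGI change near zero as little or no benefit. It could equally come from children who were doing well on mexiletine at entry and continued to do well. There is also a practical risk. Section 5.1, item 6, places the proposed efficacy assessments at screening, where performed, so a site could be asked to rate a drug the child has not yet taken.

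**Working it through.** The protocol gives no figure to reproduce and no test or sample size that rests on the CGI. The check sets the definition against the planned analysis and the entry criteria.

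**Step 1: what is rated.** Item VII grades efficacy in four ordered categories. It does not grade severity of myotonia.

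**Step 2: when baseline is.** It is the initial visit (section 3.2).

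**Step 3: who is present at that visit.** Inclusion criterion 4 allows two groups. Section 5.1 also treats the population as mixed: item 16 applies only to those previously prescribed mexiletine.

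| Status at initial visit | Baseline CGI | Change to Week 104 | Meaning |
|---|---|---|---|
| Not yet on mexiletine | None possible | Undefined | None |
| Already on mexiletine | Possible, on treatment | Can be formed | Drift between two on-treatment ratings |

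**Step 4: can the missing baseline be recovered?** No. Retrospective collection starts at the first mexiletine prescription (section 3.2), so it holds no pre-treatment rating. A value entered for an untreated child would have to rate something else, for example an earlier anti-myotonia drug (section 5.1, item 17). It would then not be comparable with a later rating of mexiletine.

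**Step 5: what the change shows in children already treated.** Four categories at each of two times give 4 × 4 = 16 possible pairs, of which 4 are no change. These 4 include *very efficient* at both visits and *poor* at both visits. A child who enters in the top category can only stay level or fall. This holds whether the change is shown as a number or as a shift between categories.

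**Step 6: how many are affected.** The protocol does not state the split. Assume k of the minimum 10 are already treated. At most k can then have a baseline rating, and at least 10 − k cannot:

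- k = 0: at most 0 of 10 have a change
- k = 5: at most 5 of 10
- k = 10: at most 10 of 10

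These are upper limits, because Assessment of Efficacy says the tests are not mandated.

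**Step 7: pooling.** The synopsis plans analysis for all patients and by age cohort, not by treatment status at entry. The pooled change would therefore come only from children already treated but be presented as a result for the whole population.

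**The case against.** The strongest reply is that most of what is needed is already planned. The sentence in section 8.13 begins with the observed CGI values, and section 8.9 promises frequencies and percentages for categorical variables. Those counts do separate sustained success from sustained failure. This stands, and it confines the defect to the change statistic. A reader might infer that the CGI cannot inform the efficacy objective at all; the planned observed values show otherwise.

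Second, baseline is enrolment, and children already on mexiletine can be rated then. Whether an effect is maintained over two years is a fair descriptive question for a registry. This also stands. A reader might infer that the change is undefined for everyone, but inclusion criterion 4 does not support that.

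One could go further and argue that every child is already treated, since section 3.1 speaks of patients being treated and section 1.4 says the prescribing decision precedes inclusion. This does not remove the problem. A decision to prescribe is not a dose taken, and criterion 4 expressly admits children still under consideration.

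Third, the method of summarising the change is left to the SAP. A reader might infer that ordered categories will be subtracted as numbers, but the protocol nowhere says so, and a shift table is possible. However, no SAP can supply a pre-treatment value on a scale that rates treatment effect.

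Two further inferences lack support. The protocol does not say that the CGI is the only scale usable at every age. The absence of the MRC scale from section 8.13 is not an omission of its analysis, because section 8.9 covers all collected parameters.

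Finally, section 8.10 leaves missing values missing, so children without a baseline rating would drop out of this summary and no value would be imputed for them. That limits the harm but does not make the summary interpretable.

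**Conclusion.** The point holds for the change statistic. The planned CGI change from baseline is undefined for children who start mexiletine at or after enrolment. For children already treated it is a difference between two on-treatment ratings that does not measure benefit over the untreated state. The pooled summary cannot be interpreted as an efficacy result.

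The impact is moderate. The CGI is one of two named efficacy scales among the primary variables, and efficacy is part of the primary objective. But efficacy is exploratory, section 1.3 rules out hypothesis testing, no decision or sample size depends on the CGI, and the observed values remain usable. The number of children affected is unknown and could be anywhere from none to all of the minimum 10.

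The conclusion rests on item VII being the complete definition of the CGI. If the data collection form holds a separate severity item for use at entry, the protocol should say so.

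**What to change.** Delete the CGI change from baseline in section 8.13 and in the synopsis. Rely on counts and percentages in each category at each on-treatment visit, separately for caregiver and investigator. This needs wording only and no new data.

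If a change is to be kept, restrict it to children already on mexiletine at the initial visit, show it as a shift between categories, and label it maintenance of effect.

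If change from the untreated state is wanted, define a separate global severity rating that can be scored at entry, before treatment in new starters. This adds one item to the data collected, and it has to be in place before those children are enrolled because it cannot be recovered later.

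The cost of the first two options is that one descriptive summary is lost or narrowed. A summary of the proportion in the upper two categories with an exact interval could be added but is optional.

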8.14 Safety Analysis

All summaries of adverse events will use only treatment emergent adverse event (TEAE) records.

In general, events will be described by counts and percentages.

Following information will be summarized for TEAEs.

- Overall Summary of TEAEs
- TEAEs by preferred term and System Organ Class (SOC)
- Treatment Related TEAEs by preferred term and SOC
- TEAEs by preferred term and SOC, Maximum Severity and Relationship
- Serious TEAEs by preferred term and SOC

• TEAEs leading to discontinuation of study drug by preferred term and SOC

Also, listing of all adverse events will be provided. The listing will include Adverse event number, description, preferred term, SOC, Start and End Date, Seriousness, Frequency of Occurrence, Severity, Action taken regarding study treatment, outcome, relationship to study treatment.

When collected laboratory and vital signs parameters will be summarised descriptively. Laboratory tests done at screening will be considered baseline.

9 DATA MANAGEMENT

9.1 Data Handling

This is a non-interventional observational study performed according to the routine regular practice at the discretion of the treating physician following recognised treatment practices for patients with myotonias. Within these constraints, and when collected, data will be recorded at the site in source documents and transcribed on to the eCRFs. The investigator shall verify the accuracy of data in the eCRF.

The investigator must maintain source documents for each patient in the study, consisting of case and visit notes (hospital or clinic medical records) containing demographic and medical information, laboratory data, electrocardiograms, and the results of any other tests or assessments. All information on CRFs must be traceable to these source documents in the patient's file. The investigator must also keep the original informed consent form signed by the patient's parents or legal guardians (a signed copy is given to the patient's parents or legal guardians).

Lupin monitoring standards require full verification for the presence of informed consent, adherence to the inclusion/exclusion criteria, documentation of SAEs, and of data that will be used for all primary variables. Additional checks of the consistency of the source data with the CRFs are performed according to the study-specific Registry Monitoring Plan. No information in source documents about the identity of the patients/subjects will be disclosed.

Data from external sources (such as laboratory data) will be appropriately handled into the database. Medical information will be coded using MedDRA and WHO DD.

Data Collection

Designated investigator staff will enter the data into the CRFs using fully validated secure webenabled software that conforms to US CFR 21 Part 11 requirements. Designated investigator site staff will not be given access to the system until they have been trained.

Automatic validation procedures within the system check for data discrepancies during and after data entry and, by generating appropriate error messages, allow the data to be confirmed or corrected online by the designated investigator site staff. The Investigator must certify that the data entered into the electronic Case Report Forms are complete and accurate. After database lock or when a site is closed, the investigator will receive copies of the patient data for archiving at the investigational site.

The Principal Investigator is responsible for assuring that the data entered by the site personnel into CRF is complete, accurate, and that entry and updates are performed in a timely manner.

10 CLINICAL STUDY MANAGEMENT

10.1 Conduct of the Study

Lupin Europe GmbH will conduct the study according to written standard operating procedures to ensure that the study is conducted and data are generated, documented and reported in compliance GCP, applicable regulatory requirements and with the site clinical practice, and when feasible given the nature of an observational study also according to ICH.

10.2 Direct Access to Source Data

During the course of the study, the monitor will visit study sites to review protocol compliance, compare eCRFs and individual patient medical records, assess drug accountability records and ensure that the study is being conducted according to applicable regulatory requirements. The review of medical records will be performed in a manner to ensure that patient confidentiality is maintained.

A review of the eCRFs for completeness, accuracy, legibility, timeliness and clarity, as well as with source documents will be required to monitor the progress of the study. Moreover, the applicable regulatory authorities, Institutional Ethics Committees (IECs) and/ or the sponsor designated Clinical Quality Assurance team may perform source data checks and/ or on-site audits/ inspections to confirm the validity of the trial conduct and the integrity of data collected. Direct access to the source data will be required for these inspections and audits; these will be carried out giving due consideration to data protection and medical confidentiality. The investigator must ensure provision of the necessary support to the sponsor/ sponsor's representative, regulatory or the IEC at all times.

10.3 Amendments to the Protocol

Important changes to the protocol and study design require a mutual agreement between the investigator and sponsor and will be effective following approval of the IEC and regulatory authorities (as necessary). These changes are to be described in the revised protocol and a list of changes detailing the pre-change and post-change versions will be prepared.

10.4 Guidance and Supervision of Sub-Investigators

The principal investigator shall maintain the list of appropriately qualified sub-investigators and study support staff (e.g., pharmacists, nurses and other staff) to whom significant trialrelated duties have been delegated.

The principal investigator shall ensure that all sub-investigators and study support staff participating in the trial are adequately trained on the protocol, the study medication and their trial-related duties and functions and they are timely informed of any new information pertaining to the study.

